3.2. Protocol Violations

At the discretion of the sponsor, major protocol violations as determined by a review of the data prior to the database locks or unblinded interim analysis and the conduct of statistical analyses may result in the removal of a subject's data from the Efficacy Evaluable Population. The sponsor, or designee, will be responsible for producing the final protocol violation file (formatted as a Microsoft Excel file), in collaboration with Cytel and the data monitoring group as applicable; this file will include a description of the protocol violation, and clearly identify whether or not this violation warrants exclusion from the Efficacy Evaluable Population. This file will be finalized prior to the database locks.

All protocol violations will be presented in the data listings.

4. STATISTICAL METHODS

4.1. Sample Size Justification

Sample size for this study was determined based on the results from the phase 2a study. In the phase 2a study, efficacy was demonstrated in 34 subjects treated with ENT-01, with a mean change from baseline in CSBMs of 2.4.

For the first part of the study it was anticipated that, out of the 72 randomized subjects, 64 (89%) will be evaluable for the primary efficacy endpoint analysis. Assuming an increase from baseline in weekly CSBM rate in the Fixed Dose period of 2.4 and 0.5 for the ENT-01 and placebo-treated subjects, respectively, and a standard deviation (SD) of 2.0, the study has 90% power to detect a difference between the treatment groups. This power estimate is based on a 2-sided t-test at the 0.05 significance level.

For the second part of the study, enrolling an additional 80 patients in a 1:1 randomization will yield a conditional power of approximately 90%. This is based on the additional subjects having a mean (SD) change from baseline for the Fixed Dose Period of 3.6 (4.11) and 1.3 (2.38) for ENT-01 and placebo, respectively. These parameter estimates are based on the results of the initial cohort of patients in the Phase 2b study. These parameter estimates are based on results of the initial cohort of patients in the Phase 2b study. Eighty additional patients will be randomized to ensure 60 evaluable patients.

4.2. General Statistical Methods and Data Handling

General Methods

All outputs will be incorporated into Microsoft Excel or Word files, sorted and labeled according to the International Conference on Harmonisation (ICH) recommendations, and formatted to the appropriate page size(s).

Tabulations will be produced for appropriate demographic, baseline, efficacy, pharmacokinetic and safety parameters. For categorical variables, summary tabulations of the frequency and percentage within each category (with a category for missing data) of the parameter will be presented. For continuous variables, the mean, median, SD, minimum and maximum values will be presented. Time to event data will be summarized using Kaplan-Meier Methodology using 25th, 50th (median), and 75th percentiles with associated 2-sided 95% confidence intervals, as well as percent of observed event rate and summary statistics for the follow-up time.

Formal statistical hypothesis testing will be performed on the efficacy endpoints with all tests conducted at the 2-sided 0.05 level of significance. Summary statistics will be presented, as well as confidence intervals on selected parameters, as described in the sections below.

For all analyses, baseline will be defined as the most recent measurement prior to the date and time of the administration of ENT-01 or placebo. Therefore, baseline may be on the same day as the dose of study treatment, but prior to the administration of the study treatment.

Computing Environment

All descriptive statistical analyses will be performed using SAS statistical software (Version 9.4), unless otherwise noted. Medical History and Adverse Events will be coding using the latest MedDRA version available upon the study start. Concomitant medications will be coded using the latest World Health Organization (WHO) Drug version available upon the study start.

Methods of Pooling Data

Not applicable to the present study.

Adjustments for Covariates

Statistical analyses for the efficacy endpoints will be adjusted by the randomization strata, the baseline CSBM rate (0 – 0.9 vs. 1.0 – 3.0).

Multiple Comparisons/Multiplicity

Adjustments for multiplicity will not be made for this study.

Subpopulations

The primary and secondary efficacy endpoints will be summarized by the subgroups based on the baseline CSBM rate (i.e., 0 - 0.9 or 1.0 – 3.0). Additionally, the primary and secondary endpoints will be presented by first and second “cohort” (i.e., the 1st cohort of subjects enrolled under the first part via the 3:1 randomization scheme; and the 2nd cohort of subjects randomized via the 1:1 randomization scheme).

Withdrawals, Dropouts, Loss to Follow-up

Subjects who withdrew from the study were not to be replaced.

Missing, Unused, and Spurious Data

When deriving endpoints that use dates, for dates that include missing values, the following conventions will be used.

Value	Imputation
Missing day, month, and year	Not imputed
Missing day and month	Day imputed to June 30th
Missing day	Day imputed to the 15th

When using dates from drug administration pages for the purposes of deriving treatment exposure, the following conventions will apply:

- If the start date is missing, it will be assumed that the first drug intake was given at the date of randomization. This date will replace all first administration missing dates.
- If the last administration date is missing, the date will be imputed with the date taken from the “Status of the Patient at the End of the Treatment” eCRF page (Date of last treatment) or if missing, with the date of last contact taken from the “Status of the Patient” eCRF page.

For missing or partial missing onset dates for adverse events, the following conventions will apply:

The start dates for AEs are important for the following:

1. Treatment-emergent adverse event (TEAE) algorithm. A TEAE is an event that first occurred or worsened in severity after baseline.
2. Designation of unique AE occurrences.
3. Completely missing or partially missing AE onset dates will be imputed after due diligence to obtain accurate AE information has failed. The imputation will consider the start and stop dates relative to each other, and relative to the date of consent and date of first dose.

AEs with start dates that are completely or partially missing will be analyzed as follows:

- If the start date of an event is completely missing, then the event is assumed to be treatment-emergent.
- If the start date has the month and year but day is missing, the event will be considered treatment-emergent if the month and year of the start date of the event are equal to, or greater than, the month and year of the date of first dose of study drug.

If the start date has the year, but day and month are missing, the event will be considered treatment-emergent if the year of the start date of the event is the same as, or later than, the year of the date of the first dose of study drug.

Visit Windows

No visit windows will be applied.

4.3. Interim Analyses

An unblinded interim analysis will be performed after the last subject completes the Fixed Dose period.

4.4. Subject Disposition

Patient disposition, including analysis population allocation, patients enrolled, completed, and discontinued, and primary reason for discontinuation, will be summarized using frequency and percent. For the purposes of reporting, patients who complete the Fixed Dose period are considered to have completed the trial.

Analysis populations, patients who completed each period (fixed dose, single blind, and washout), and patients who discontinued the study and reasons for discontinuation will be summarized by randomized treatment (placebo or ENT-01). The disposition of subjects in the mITT and safety populations up to the end of the fixed dose period will also be summarized by summarizing the number of subjects who completed the fixed dose period or discontinued study during the fixed dose period, along with the reason for discontinuation. This summary will be done by dose during the fixed dose period. Patients will be counted in every dose that they received during the fixed dose period.

Patients who give informed written consent but are not randomized are considered screen failures. Minimal data, such as demographic information and the reason for screen failure, for patients who fail screening will be recorded on the IXRS. Reasons for screen failure will be summarized.

A by-subject listing of study completion information, including the reason for premature treatment and study discontinuation, if applicable, will be presented.

4.5. Demographic and Baseline Characteristics

Demographics, baseline characteristics and medical history will be summarized for the safety, mITT and fixed dose populations by treatment group (placebo and fixed dose ENT-01) and data listings will be provided as well. Demographic variables, including age, gender, race, ethnicity height, weight, and BMI will be summarized in tabular form. Age (years) will be calculated as (date of informed consent – date of birth +1) / 365.25. Baseline characteristics include age at diagnosis of Parkinson's disease, years with Parkinson's disease, years of constipations, Hoehn and Yahr stage, and constipation severity using baseline CSBM rate.

4.6. Efficacy Analyses

Efficacy analyses to evaluate the treatment effect will be conducted using the Fixed Dose population as the primary population. The analyses will also be performed using the mITT and Efficacy Evaluable populations. Summary statistics will also be presented.

The comparison of active versus placebo treatment will be tested at the two-sided 0.05 significance level.

The date of randomization will not be included for either baseline or post-baseline weekly efficacy endpoints (i.e., rates or mean values). Similarly, the date of the single-blind period visit will also not be used in derivation of weekly efficacy endpoints (rates or mean values). Also, the visit 5 Date (ie, the date the patient begins the Washout period) will be included in the single-blind period (i.e., the single-blind period lasts from the day after Visit 4 up to and including Visit 5).

4.6.1 Derivation of Weekly CSBM and SBM Rates

There are 4 CSBM Definitions, each of which are based on the set of questions from the patient's daily diary. The rates from each of the CSBM definitions will be presented. Note: since the assessments are different between the 2 cohorts the definitions are different.

CSBM Definition 1:

A CSBM is a BM which meets each of the following 3 criteria.

For the 1st Cohort of patients:

- 1) For this BM the patient responded "No rescue medication used" to the query "Have you used rescue medication within 24 hours prior to this bowel movement?"
- 2) For this BM the patient responded
 - "Yes" to the query "Did you feel like you completely emptied your bowels?"
OR
 - "No" to the query "Did you feel like you completely emptied your bowels?" but the BSFS Ease of Passage score is 6 or 7.
- 3) The bowel movement has a BSFS Ease of Passage score of 3 or greater (or missing).

For the 2nd Cohort of patient:

- 1) No rescue mediation was taken within 24 hours of the Bowel Movement (note: the date and time of the bowel movements and rescue medication (i.e., laxative) use are included in the subjects daily diary data).
- 2) For this BM the patient responded :
 - “No” to the query “Do you feel like you have more poop left to pass?”OR
 - “Yes” to the query “Do you feel like you have more poop left to pass?” and the BSFS Ease of Passage score is 6 or 7.
- 3) The bowel movement has a BSFS Ease of Passage score of 3 or greater (or missing).

CSBM Definition 2:

The 2nd CSBM definition removes the BSFS criteria from the CSBM definition. A CSBM is a BM which meets each of the following 2 criteria

For the 1st Cohort of patients:

- 1) For this BM the patient responded “No rescue medication used” to the query “Have you used rescue medication within 24 hours prior to this bowel movement?”
- 2) For this BM the patient responded “Yes” to the query “Did you feel like you completely emptied your bowels?”

For the 2nd Cohort of patient:

- 1) No rescue mediation was taken within 24 hours of the Bowel Movement (note: the date and time of the bowel movements and rescue medication (i.e., laxative) use are included in the subjects daily diary data).
- 2) For this BM the patient responded “No” to the query “Do you feel like you have more poop left to pass?”

CSBM Definition 3:

The 3rd CSBM definition broadens the definition of a CSBM for the 2nd cohort. A CSBM is a BM which meets each of the following 2 criteria

For the 1st Cohort of patients:

- 1) For this BM the patient responded “No rescue medication used” to the query “Have you used rescue medication within 24 hours prior to this bowel movement?”
- 2) For this BM the patient responded “Yes” to the query “Did you feel like you completely emptied your bowels?”

For the 2nd Cohort of patient:

- 1) No rescue mediation was taken within 24 hours of the Bowel Movement (note: the date and time of the bowel movements and rescue medication (i.e., laxative) use are included in the subjects daily diary data).
- 2) For this BM the patient responded
 - “No” to the query “Do you feel like you have more poop left to pass?”
OR
 - “Yes” to the query “Are you Done for the Day”
OR
 - “Yes” to the query “Did you feel like you completely emptied your bowels?”

CSBM Definition 4:

This is a more stringent definition for CSBMs for Cohort 2, requiring each of the 3 completeness questions to be appropriately answered. A CSBM is a BM which meets each of the following 3 criteria.

For the 1st Cohort of patients:

- 1) For this BM the patient responded “No rescue medication used” to the query “Have you used rescue medication within 24 hours prior to this bowel movement?”
- 2) For this BM the patient responded
 - “Yes” to the query “Did you feel like you completely emptied your bowels?”
OR
 - “No” to the query “Did you feel like you completely emptied your bowels?” but the BSFS Ease of Passage score is 6 or 7.
- 3) The bowel movement has a BSFS Ease of Passage score of 3 or greater (or missing).

For the 2nd Cohort of patient:

- 1) No rescue mediation was taken within 24 hours of the Bowel Movement (note: the date and time of the bowel movements and rescue medication (i.e., laxative) use are included in the subjects daily diary data).
- 2) For this BM the patient met either of these 2 criteria:
 - 2a) The patient responded:
 - “No” to the query “Do you feel like you have more poop left to pass?”
AND
 - “Yes” to the query “Are you Done for the Day”
AND
 - “Yes” to the query “Did you feel like you completely emptied your bowels?”
OR
 - 2b) The BSFS Ease of Passage score is 6 or 7.

3) The bowel movement has a BSFS Ease of Passage score of 3 or greater (or missing).

An SBM is a BM which meets the following criteria:

- For this BM the patient responded “No rescue medication used” to the query “Have you used rescue medication within 24 hours prior to this bowel movement”

A patient’s CSBM weekly rate over a particular period will be derived using the following algorithm:

Weekly CSBM Rate = $7 \times \{\# \text{ of CSBMs in the period}\} / \{\# \text{ of days in the period}\}$

The weekly SBM rate calculations use the same algorithm.

If a patient is missing BM information for a day, it will be assumed that the patient had 0 SBMs and 0 CSBMs for that period (with the exceptions in calculating Baseline CSBM and SBM rates noted in Section 2.6).

If a subject diary has “repeat” stool data (eg, a BM repeated with the same date/time of BM) only the latest duplicate observation relative to when the patient entered the data into the diary will be used.

For the calculation of the Baseline CSBM (SBM) weekly rate:

- If the patient has more than 14 days of diary data during the Screening Period, only the last 14 days with non-missing diary entries prior to the randomization visit will be used (i.e., the days which are more than 14 days prior to the randomization visit will be excluded)
- If a patient has 11- 14 days of diary data, all available diary days will be used.
- If a subject has more than two weeks of entries during the screening period, consecutive missing entries during the screening period will be excluded from baseline calculations, and the last fourteen days with entries during the screening period will be used to derive baseline weekly rates.

For analyses of the CSBM (SBM) in the Fixed dose period, if a patient has not been in the Fixed Dose period for at least seven days, then the number of days used for calculating the weekly CSBM (SBM) rate will be adjusted to seven days by using the last “n” days of the Dose Escalation period leading up to the fixed dose period to get to 7 days in the Fixed Dose period. This derivation will be used for all efficacy endpoints for the Fixed Dose Period (e.g., stool ease of passage and stool consistency).

For analyses of the CSBM (SBM) rate during the single-blind placebo and washout periods, all available data in those periods, excluding observations on the date of the single-blind placebo visit as described before, will be used in the derivations of weekly rates described at the beginning of this section.

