2.6. Efficacy, Pharmacokinetic, Safety and Tolerability Endpoints

2.6.1 Efficacy Endpoints

Primary Efficacy Endpoint

The primary efficacy endpoint is the change from baseline in the weekly CSBM rate during the Fixed Dose period.

Baseline is defined as the weekly CSBM rate during the 2-week screening period. If a subject has more than two weeks of entries during the screening period, consecutive missing entries during the screening period will be excluded from baseline calculations, and the last fourteen days with entries during the screening period will be used to derive baseline weekly rates.

Subjects with fewer than 11 days of diary data during screening would be excluded from the study. The primary efficacy endpoint will be obtained as the weekly CSBM rate during the Fixed Dose period with exceptions as noted in section 4.7. The frequency of CSBMs will be

determined via a web-based electronic diary where the passage of a bowel movement or absence thereof will be recorded daily throughout the study by the subject.

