4.6.3 Analysis of the Primary Efficacy Endpoint

The primary efficacy endpoint is the change from baseline in weekly CSBM rate during the Fixed Dose period. The primary analysis will be based on the Fixed Dose Population. The primary efficacy analysis will be performed via an analysis of covariance (ANCOVA) model with change from baseline in weekly CSBM rate as the dependent variable, treatment (ENT-01 or placebo) as the independent variable, and baseline weekly CSBM rate as a covariate.

As a supplemental analysis, the treatment effect for the primary efficacy endpoint will be summarized by the weekly CSBM rate subgroups (0 – 0.9, 1.0 – 3.0). The analysis will be performed for both Efficacy Evaluable population and Fixed Dose population.

The study will be considered a success if the p-value for the comparison of treatment groups from the ANCOVA model using the Fixed Dose population is significant (p<0.05).

Change from baseline in weekly CSBM rate will also be summarized by the specific fixed dose for patients. These summaries will be descriptive in nature only and no inferential statistics will be performed.

A linear trend test for weekly CSBM rate within each treatment group across baseline, fixed dose, and single blind periods will be conducted by using mixed model repeated measures (MMRM) methods, where the Baseline, Fixed Dose, and Single Blind periods are assigned values of 0,1, and 2 respectively for modeling purposes. Baseline CSBM rate (0-0.9/1.0-3.0) is included as a factor, with subject intercept and slope as random effects in the mixed model. The trend test will also be conducted across all subjects, including both Placebo and ENT-01 treatment groups in the model as a factor (fixed effect).

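### The SAP lists four CSBM definitions, ties none to the p<0.05 success rule, and for cohort 2 none matches the protocol, yet it declares no changes.

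*SAP*

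**What the plan says.** SAP 2.6.1 states: "The primary efficacy endpoint is the change from baseline in the weekly CSBM rate during the Fixed Dose period". SAP 4.6.3 adds: "The study will be considered a success if the p-value for the comparison of treatment groups from the ANCOVA model", in the Fixed Dose population, is below 0.05. Neither section says how a CSBM is identified.

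SAP 4.6.1 does that in four ways and states "The rates from each of the CSBM definitions will be presented". For cohort 2:

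- **Definition 1:** no rescue within 24 hours; no more left to pass, with an exception for a stool reported as unfinished "and the BSFS Ease of Passage score is 6 or 7"; and criterion 3 ("The bowel movement has a BSFS Ease of Passage score of 3 or greater (or missing"). Cohort 1 has a parallel exception for a stool reported as not completely emptied, "but the BSFS Ease of Passage score is 6 or 7".
- **Definition 2:** no rescue and no more left to pass. The SAP introduces it thus: "The 2nd CSBM definition removes the BSFS criteria from the CSBM definition".
- **Definition 3:** no rescue, and any one of three favourable completeness answers (nothing left to pass, done for the day, completely emptied).
- **Definition 4:** introduced as stricter, "requiring each of the 3 completeness questions to be appropriately answered". Its rule 2b nevertheless accepts any non-rescue stool scored 6 or 7, whatever those answers were.

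The protocol has three wordings, all excluding stools that follow rescue medication or taking that exclusion as given:

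- Section 3.1, beside the primary endpoint: done for the day, no more left to pass, and not Bristol type 1 or 2.
- List of Abbreviations: no more to pass and completely emptied, with no stool-form rule.
- Section 4.1 diary training: completely emptied, no more left, and not just pebbles.

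SAP section 5 reports no changes from the protocol-defined analyses.

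**The concern.** A single-test success rule needs a dependent variable that is fixed in writing. Here the variable has four candidate forms, and the choice among them is left to inference. That would be a drafting gap if the implied choice followed the protocol. It does not: Definition 1 counts stools that protocol 3.1 excludes, and section 5 says nothing changed.

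The same undefined count feeds the prokinetic response and the time to first CSBM. The documents also do not say which definition the central system used for baseline rates (protocol 4.2), which decide eligibility and stratum, or which one produced the planning values of 3.55 and 1.28 (protocol 9.2.5). Cohort 1 had already been analysed unblinded (protocol 9.2.6), so a choice made now is not blind to that part of the data.

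**Working it through.** The plan gives no figure on this point to reproduce. The checks are a comparison of the definitions and the arithmetic of one stool.

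**1. Do any of the definitions agree with the protocol?** Take a non-rescue stool in cohort 2. Three yes/no completeness answers and four score classes (1-2, 3-5, 6-7, missing) give 2 × 2 × 2 × 4 = 32 patterns. Read the score as Bristol, read pebbles as Bristol 1-2, and treat a missing score as not 1-2. Protocol 3.1 then counts 6 patterns, the Abbreviations wording 8 and the 4.1 wording 6.

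| SAP rule | Patterns counted | Mismatches with 3.1 (added/dropped) | With Abbreviations | With 4.1 |
|---|---|---|---|---|
| Definition 1 | 16 | 10 (10/0) | 12 (10/2) | 10 (10/0) |
| Definition 2 | 16 | 10 (10/0) | 8 (8/0) | 10 (10/0) |
| Definition 3 | 28 | 22 (22/0) | 20 (20/0) | 22 (22/0) |
| Definition 4 | 10 | 8 (6/2) | 10 (6/4) | 8 (6/2) |

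Definition 1's ten additions to 3.1 are 6 patterns with nothing left to pass but not done for the day (2 emptied answers × 3 score classes), plus 4 override patterns (more left to pass, score 6-7). Definition 4 adds 6 through rule 2b and drops 2 because it also asks for completely emptied. Pairs of SAP definitions differ from each other in 6 to 20 patterns. These are counts of possible answers, not frequencies.

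Treating a missing score as failing the Bristol rule would not produce a match with 3.1, because every SAP definition can count a stool with a missing score.

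**2. Which definitions count stools reported as incomplete?** Of the 16 patterns in which the patient says more is left to pass, Definition 1 counts 4, Definition 2 none, Definition 3 counts 12 and Definition 4 counts 4. A stool that is unfavourable on all three questions but scored 6-7 is counted by Definitions 1 and 4. In cohort 1, where the SAP shows one completeness question, Definitions 1 and 4 coincide and both carry the override; Definitions 2 and 3 coincide without it.

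**3. What is one stool worth?** SAP 4.6.1: rate = 7 × CSBMs / days.

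- 25 days: 7/25 = 0.28 per week
- 14 days: 7/14 = 0.50
- 7 days, the SAP minimum: 7/7 = 1.0, the whole increase that defines a prokinetic response in SAP 2.6.2

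At baseline (11 to 14 diary days), one counted stool gives 7/14 = 0.50 to 7/11 = 0.64, and two give 14/14 = 1.00 to 14/11 = 1.27. Reclassifying one of two stools therefore crosses the 0.9/1.0 stratum boundary.

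**4. Illustration only.** Suppose the counting rule adds a constant net excess on ENT-01, after placebo and baseline, and the SD stays at 3.88 (protocol 9.2.5). The excess that moves the chance of a significant result favouring ENT-01 from 0.025 to 0.05, with no other effect, is (1.960 − 1.645) × SE:

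- 36 per arm (40 less 10%): SE = 3.88 × √(2/36) = 0.9145; excess 0.29 per week
- 30 per arm (60 evaluable): SE = 3.88 × √(2/30) = 1.002; excess 0.32
- cohorts pooled, 10% loss (84.6 and 52.2): SE = 0.683; excess 0.22

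Nothing in the documents says whether an excess of this size occurs.

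**The case against.** The best defence is that Definition 1 is evidently primary: Definition 2 removes something from it, Definition 3 broadens and Definition 4 tightens. Four rates are presented, but SAP 4.6.3 sets one p-value. This stands in part. A reader might infer that the SAP plans four chances at success; the text does not support that, so no inflated error rate should be attributed to the plan. But if Definition 1 is primary, it still departs from protocol 3.1 in 10 of 32 patterns, undeclared.

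Second, the protocol is itself inconsistent. That is true, and the mismatch is not the SAP's fault alone. Even so, no cohort 2 definition matches any of the three wordings.

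Third, the score label combines the Bristol scale (protocol Appendix 6) with ease of passage (Appendix 5). A reader might infer that 6-7 means urgent with pain or incontinent. Bristol is much more likely: the SAP speaks of BSFS criteria, and a threshold of 3 mirrors the protocol's exclusion of types 1 and 2. The label needs correcting, but the point does not depend on the remote reading.

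Fourth, the override applies in both arms and at baseline, and Definitions 2 and 3 will show results without it. A reader might infer that it favours ENT-01. On the Bristol reading it would do so only if ENT-01 produces more loose stools reported as incomplete than placebo does, and the documents give no such frequencies.

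**Conclusion.** The point holds. No definition is tied to the success rule, the implied one departs from the protocol, and section 5 says there are no departures. This is an error in the plan as written, more than missing detail, and it must be corrected before the final analysis.

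It should be stated no more strongly than this. Definition 1 is a strongly implied reference, so it would be wrong to say that the reader has no guide. At least two definitions count stools reported as incomplete: 1 and 4 through an override found nowhere in the protocol, and 3 by accepting any one favourable answer. In Definition 4 the override contradicts its own introduction.

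The direction and size of the effect on the treatment comparison are unknown. What is firm is the leverage of one reclassified stool, 0.28 to 1.0 CSBM per week for a subject. The lower figure applies only to someone whose Fixed Dose period spans all 25 days. The pattern counts rest on the Bristol reading and the stated handling of missing scores.

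**What to change.** 1. Reconcile the three protocol wordings (List of Abbreviations, 3.1, 4.1).
2. In SAP 4.6.1 and 4.6.3, name one primary definition for the success rule and every CSBM-based endpoint. It should follow the reconciled wording without the 6-7 override. For cohort 1, use the single completeness question that the SAP shows.
3. State how missing stool scores are treated, since the SAP now lets them pass. Correct the scale label to Bristol stool consistency if that is what is meant.
4. Label the other definitions, including those with the override, as sensitivity analyses that carry no success claim.
5. In SAP section 5, record each departure from the protocol and that the choice was made after cohort 1 was unblinded. State which definition produced the planning values and the centrally calculated baseline rates.
6. Keep the strata as randomised, even where a re-derived baseline falls on the other side of the boundary.

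The cost is SAP and protocol wording plus re-derivation of rates from diary items already collected. The treatment difference and the planning inputs may change by an amount that cannot be foreseen, and the cohort 1 part of the choice cannot be made blind.
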